8.9 ONGOING PROMOTER SUPPORT AND TRAINING

Up to visits 8-11 for up to n=70 promoters in the intervention arm only

Promoters in the intervention group will be invited for up to four additional training sessions in which they will be encouraged to motivate men in their network who initiated PrEP or ART to come to clinics for periodic medication refills and consultations. Promoters will be given up to KSH 1000 (~\$10) for their participation in each additional full day of follow up training.

8.10 TEXT MESSAGE REMINDERS

To the extent that men on PrEP and ART are willing, optional cell phone appointment reminders and text messages motivating adherence will be sent to them (including promoters). These messages will be motivational, will not include any identifying information and will include generic texts such as "maintain your good health", to cater for status-neutral language that can work for both HIV positive individuals taking ARVs, as well as HIV-negative individuals on PrEP who may need adherence support.

Sample language for these text messages are included in the table below. These sample texts will be further refined with the input of the community and our peer leaders to ensure that they are locally and culturally salient and relevant. We will ensure these messages are status-neutral and non-stigmatizing to ensure they are relevant and do not compromise patient confidentiality.

Table 4. Sample Text Messages to Facilitate Adherence

It is important to maintain your health.
Please prioritize your health and well-being to stay strong.
Please remember your appointment.
If you need support to make your appointments, please reach out to your provider.
Your provider can help keep you healthy, please reach out if you need help.
Be healthy, have a healthy happy family!
Be healthy, be productive!

8.11 INCENTIVES AND STUDY PAYMENTS

Incentive Type	Amount	Recipient	Purpose
Cash (in-person) or Mpesa (for phone surveys)	500ksh (~\$5)	All participants who take part in the pilot survey – either in person or phone	To offset time/wages lost due to participation in survey data collection
Cash (in-person) or Mpesa (for phone surveys)	500ksh (~\$5)	All participants who take part in the pilot survey and are then randomly selected for interviews – either in person or phone	To offset time/wages lost due to participation in survey data collection
Cash	500ksh (~\$5)	All participants who take part the social network survey to be mapped	To offset time/wages lost due to participation in social network survey
Cash	500ksh (~\$5)	All control and intervention participants who are mapped and randomized in the study and who participate in the baseline survey	To offset time/wages lost due to participation in survey data collection
Cash	500ksh (~\$5)	All control and intervention participants who take part in the 3 month follow up survey	To offset time/wages lost due to participation in 3 month survey data collection
Cash	500ksh (~\$5)	All control and intervention participants who take part in either the in-depth interviews or focus group discussions- incentivized per data collection method	To offset time/wages lost due to participation in data collection

Table 5 Details of Incentive Types, Amounts, Populations, and Purpose

Voucher	500ksh (~\$5)	Only intervention participants who have used a HIVST and bring in their voucher to the health facility for cash redemption	To encourage confirmatory HIV test and off set travel to facility
Cash	1000ksh (~\$10) 500ksh (~\$5) 200ksh (~\$2)	Only intervention and control participants selected to be promoters and those who participate in the promoter training	 1000 Ksh to offset time/wages lost due to participation in trainings. 1000Ksh per day of training. 500ksh to buy airtime in order to contact men in their social networks for promotion activities Up to 200ksh to offset transport costs related to promotion activities.
Cash	500ksh	Intervention and control participants who link to care (ART) or PrEP who come in for 6 month study visit for blood and urine samples (for adherence)	500 ksh to offset transport

9 FIDELITY

9.1 PROMOTER TRAINING AND TRACKING

There may be heterogeneity in fidelity to intervention procedures by promoters (some may offer self-tests to non-network members); we will assess fidelity using follow-up survey data from promoters and network members. We will also try to achieve high fidelity by asking research team members to periodically contact promoters to check in on their activities. Adjustments, clarification, and re-training will be conducted as needed. We will collect quantitative process and fidelity measures corresponding to each of the components of the intervention through review of administrative records, and other study data. Further, we will use various tools attached to the protocol to assess the outcome of the promotor training and the extent to which the training was delivered and received as intended. Please see the appendix for the tools we will use to evaluate the training effectiveness.

Following the promoter training, the cadre of promoters will receive individual support from the study regional manager/nurse, who will conduct study check-ins at the beaches and be available by cell phone to answer questions and problem solve if issues arise. Additionally, we will use a rigorous two-phased

approach, beginning with: 1) qualitative of in-depth and key informant interview and FGD data, and 2) mixed-methods data grouped by categories defined using social network survey data, process and fidelity measures, and trial outcome data. This will involve analyzing qualitative data collected within categorized groups of participants including (but not limited to) testers vs. non-testers, linkers vs. non-linkers to ART and PrEP, virally suppressed vs. detectable VL, and PrEP adherent vs. non-adherent. This approach will allow us to identify emergent themes within groupings and to rigorously assess conceptual alignment or differences across groupings, with attention to evidence of contradictory findings and deviant cases in the data. Feedback on key recruitment, data collection and other metrics will be provided via regular data reports to study sites.

9.2 MEASURES TO MINIMIZE BIAS

The study is subject to limitations that we will take steps to address. First, it may be difficult to objectively ascertain self-test results, as we will not directly observe self-testing. However, we expect measurement error to be distributed randomly across study arms, and we will use pre-printed cluster IDs on clinic vouchers and on self-tests to validate our measurements of this outcome. Second, it may be difficult to contact mobile men for follow-up, but we will benefit from tracking procedures we are successfully using in ongoing studies and will strengthen them further by collecting contact details of trusted friends of participants. This information (names and phone numbers) will be collected using secure study forms and will be protected similar to other study data and discarded following the procedures outline in sections 12.3 and 12.4. Since these trusted friends of participants are not taking part in study activities, they will not be consented. Third, there may be heterogeneity in fidelity to intervention procedures by promoters (some may offer self-tests to non-network members); we will assess fidelity using follow-up survey data from promoters and network members. We will also try to achieve high fidelity by asking RAs to periodically contact promoters to check in on their activities. Adjustments, clarification, and re-training will be conducted as needed. Fourth, as in most community-based interventions, there is potential for cross-contamination between control and intervention social networks. Our approach to this risk is to both minimize cross-contamination and also measure the extent to which cross-contamination occurs in the trial, which in turn will allow us to model how this influences effect sizes. In our training we will emphasize that promoter efforts should be limited to members of their own close social network and not to those outside or adjacent to their network. To measure cross-contamination we will include in our surveys questions to elicit the frequency and intensity of exposure to the intervention and control condition elements. We will also assess whether men who have spatial proximity to intervention clusters are more likely to have been tested for HIV – a proven empirical approach to testing for spillover effects.

9.3 STUDY INTERVENTION/EXPERIMENTAL MANIPULATION ADHERENCE

Because promoters (study participants and members of social networks) are primarily implementing the intervention, adherence will be encouraged by training at the outset, and periodic monitoring to ensure that the correct messages on HIVST, ARV and PrEP are being disseminated as needed.

1 STATISTICAL CONSIDERATIONS

1.1 STATISTICAL HYPOTHESES

Primary Endpoint(s): self-reported HIV testing in the past 3 months by participants, as measured in the 3-month follow-up surveys.

We hypothesize that the intervention group will be more likely to test for HIV than the control group.

Primary Endpoint (s): Linkage to ART or to PrEP within about 3 months and Initiation of ART or PrEP (among those eligible), within 3 months of linkage

We hypothesize higher a proportion of participants linking to ART or PrEP (confirmatory testing and ART referral for positives, and PrEP screening for negatives among those receiving the intervention. We also hypothesize higher ART and PrEP uptake within 3 months among men in social networks assigned to the intervention group.

Primary Endpoint (s): Viral suppression (HIV RNA <400 c/mL) at 6 months and adherence to PrEP (TFV levels of >= 1500 ng/mL in urine = adequate adherence 28) at 6 months.

We hypothesize a higher proportion of individuals both retained in care and adherent to treatment in the intervention group compared to the control group.

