Outcome Measures:	 Primary outcomes Self-reported HIV testing within 3 months of intervention start Linkage to care or prevention within 3 months of intervention start Viral suppression (HIV RNA <400 c/mL) at 6 and 12 months among HIV-positive participants PrEP adherence at 6 months Secondary outcomes Initiation of ART or PrEP within 3 months confirmatory test or PrEP eligibility screening Confirmatory HIV testing uptake 3 to 6 months after intervention start
	financial incentives to offset transport costs) to other men in their close social network.

Self-Test Strategies and Linkage Incentives to Improve ART and PrEP Uptake in MenVersion 11.0November 29, 2022

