For the primary outcome, we will have \geq 80% power to detect a significant increase in viral suppression and adherence in those on ART and PrEP, respectively, assuming a proportion of successes in the control arm of 70% or greater power (*based on SEARCH trial data on viral suppression rates among fishermen and projected urine TFV detection rates of 70%, weighted for the likely number of men on PrEP (n=168) and men on ART (n=72)*). We assume the observed proportion of successes in the intervention arm will be 89% or greater using an ICC of 0.10, a design effect from clustering of 1.7, and a type-1 error rate of 5%. For the combined primary outcome of retention on ART or PrEP at 6 months (+ about 1 month), this study will have 81% or greater power to detect a significant increase in linkage assuming a proportion retained in care in control arm of 81% (*based on SEARCH data on retention rates weighted for the likely number of men on PrEP (n=168) and ART (n=72)*) if the observed proportion in intervention arm is 96% or greater using the above assumptions.

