1.3.3 ANALYSIS OF ADDITIONAL ENDPOINT(S)

Primary Outcome: the primary outcome measure will be linkage to care or prevention within 3 months of the Aim 1 intervention start. Linkage will be defined for HIV-positive participants as a documented confirmatory HIV test result, and a documented HIV clinic visit following referral. Linkage will be defined for HIV-negative participants as documented evidence of evaluation for PrEP (following standard of care procedures) extracted from medical records.

Secondary outcome: The secondary outcomes will be confirmatory HIV testing uptake 3 – 6 months after intervention start and the initiation of ART, or PrEP (among those screened as eligible), within 3 months of the confirmatory test or eligibility screening. HIV testing uptake will be measured via documented testing records in clinic records and ART start will be measured via documented prescription for ARV medications, and for PrEP start, via oral PrEP prescription.

Third outcome: The third primary outcome is a composite measure meant to capture "success" in HIV prevention and/or treatment behaviors. The measure will be defined as either adequate levels of tenofovir, indicating PrEP adherence (defined as TFV levels of >= 1500 ng/mL in urine indicating adequate adherence vs. < 1500 ng/ml) among HIV seronegative individuals who screened eligible for PrEP or the proportion of HIV-positive participants with viral suppression (defined as HIV RNA <400 c/mL using the Abbott realTime HIV-1 platform and assay, with a detectable threshold of 40 cells per microliter at 6 months. PrEP adherence will be measured at 6 months after initiation using our novel technology of point-of-care rapid testing to assess TFV adherence in urine (developed by Co-I [name] in collaboration with Alere Rapid Diagnostics[™]). For both components of the measure, we will define missing values as failure (i.e. inadequate adherence or unsuppressed).

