#### 3) Protocol version

This SAP references Owete Protocol Version 4.0, last updated May 5, 2020.

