### Section 4: Statistical Principles

### 16) Level of statistical significance:

Standard levels of significance testing will be used (p=0.05) for two sided-tests. We will report 95% confidence intervals and exact p-values (or p<0.001).

**17)** Description and rationale for any adjustment for multiplicity: (if so, detailing how the type I error is to be controlled.) Our primary outcomes were established in our protocol, and thus no adjustments will be made for multiplicity.

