## Section 6: Analysis

# 26) Outcome definitions

- a. Primary Outcomes:
  - i. Proportion of HIV testing: The first primary outcome will be the proportion of study participants who self-report HIV testing in the last three months (at the 3 month follow up visit) compared to those who self-report not using testing during the last three months.
  - ii. Proportion of HIV self-testing: The second outcome will be the proportion of study participants who self-report using the self-testing kit in the last three months (at the 3 month follow up visit) compared to those who self-report not using a self-testing kit during the last three months.
  - iii. Proportion with successful linkage to ART or PrEP within 3 months of intervention start (ie: when promoters receive self-test kits to distribute). The second primary outcome will be defined as the proportion of individuals who link to ART (if confirmatory HIV testing is positive) or PrEP evaluation (if confirmatory HIV testing is negative), meaning they present at a study facility/clinic (depending on results of HIV testing) within three months of the intervention start (defined as from when study promotors receive the kits for distribution).
  - iv. HIV treatment and prevention success: The third primary outcome is a composite measure meant to capture "success" in HIV prevention and/or treatment behaviors (ie: Viral suppression among HIV+ and adequate TFV among those prescribed PrEP). The measure will be defined as either adequate levels of tenofovir, indicating PrEP adherence (defined as TFV levels of <1500 ng/mL in urine indicating inadequate adherence vs. ≥ 1500 ng/ml) among HIV seronegative individuals who screened eligible for PrEP *or* the proportion of HIV-positive participants with viral suppression (defined as HIV RNA <400 c/mL using the Abbott realTime HIV-1 platform and assay, with a detectable threshold of 40 cells per microlitre) at 6 and 12 months. Secondary thresholds of <1000 copies/mL will also be examined. PrEP adherence will be measured at 6 and 12 months after initiation using our novel technology of *point-of-care rapid testing to assess TFV adherence in urine* (developed by Co-I [name] in collaboration with Alere Rapid Diagnostics™). For both components of the measure, we will define missing values as failure (i.e. inadequate adherence or unsuppressed).

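### Protocol and SAP disagree on which outcomes are primary, so the set on which the SAP rests its decision not to adjust for multiplicity cannot be identified

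*Protocol*

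**What the plan says.** **Testing rule.** SAP 16 states: "Standard levels of significance testing will be used (p=0.05) for two sided-tests". SAP 17 adds: "Our primary outcomes were established in our protocol, and thus no adjustments will be made for multiplicity". Neither document gives a hierarchy, a split of alpha, or a rule that several outcomes must succeed together. SAP 3 says which protocol is meant: "This SAP references Owete Protocol Version 4.0, last updated May 5, 2020". The protocol supplied is version 11.0 of November 2022.

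**Protocol.** The synopsis lists four primary items: self-reported testing, linkage, and then "Viral suppression (HIV RNA <400 c/mL) at 6 and 12 months among HIV-positive participants PrEP adherence at 6 months". It puts initiation under secondary outcomes. Section 1.1 has three primary headings, the second of which reads "Linkage to ART or to PrEP within about 3 months and Initiation of ART or PrEP (among those eligible), within 3 months of linkage". Section 1.2 gives a separate power statement that begins "For the combined primary outcome of retention on ART or PrEP at 6 months". Section 1.3.1 speaks of linkage as a secondary analysis. Section 1.3.2 names testing as the primary outcome. Section 1.3.3 makes linkage primary, makes initiation and retention secondary, and joins suppression and adherence: "The third primary outcome is a composite measure meant to capture" success in prevention or treatment, at 6 months.

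**SAP.** Section 26.a has four entries under its primary heading. Testing is called the first primary outcome. The next entry reads: "The second outcome will be the proportion of study participants who self-report using the self-testing kit". Linkage is then called the second primary outcome, and the composite, at 6 and 12 months, the third. Section 11 calls 12-month retention primary; section 26.b lists retention as secondary.

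**The concern.** Each test is run at an unadjusted 5%, so the primary label largely decides which results count as confirmatory. Leaving separate aims unadjusted is a defensible position, but it presupposes a fixed and identifiable primary set. As the text stands, someone reporting the trial could cite a section that supports calling initiation, retention or kit use primary after the results are known.

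The Aim 1 conflict affects the main test itself. SAP 27 names self-reported HIV testing as the outcome and then compares the proportions self-testing. Intervention promoters hand out kits, whereas control promoters hand out vouchers for a standard test or a kit at a facility. Kit use and any testing could therefore show quite different effects.

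**Working it through.** **Step 1. Labels side by side.**

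| Outcome | Placed under primary | Placed elsewhere |
|---|---|---|
| Any HIV testing | Synopsis, Protocol 1.1, 1.3.2; SAP 26.a.i | SAP 27 names it, then tests self-testing |
| Linkage | Synopsis, Protocol 1.1, 1.2, 1.3.3; SAP 11, 26.a.iii | Secondary analysis in Protocol 1.3.1 |
| Initiation of ART/PrEP | Protocol 1.1 | Secondary in synopsis, Protocol 1.3.3 and SAP 27 |
| Suppression; PrEP adherence | Two items in the synopsis; one composite in Protocol 1.3.3 and SAP 26.a.iv | – |
| Retention | Protocol 1.2 (6 months); SAP 11 (12 months) | Secondary in Protocol 1.3.3 and SAP 26.b |
| Self-test kit use | SAP 26.a.ii | In no primary list of the supplied protocol |

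**Step 2. Time point of the third outcome.** Protocol 1.1 and the definition in 1.3.3 give 6 months. SAP 26.a gives 6 and 12. The synopsis gives 6 and 12 for suppression but 6 for adherence.

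**Step 3. Length of each list.** Protocol 1.3.2–1.3.3: three. Synopsis: four, or five if the two suppression time points are counted. Protocol 1.1: five (testing, linkage, initiation, suppression, adherence). Protocol 1.2: four (testing, linkage, suppression/adherence, retention). SAP 26.a: four, or five with the composite at two time points. The range is three to five. Across both documents, seven distinct constructs stand under a primary heading somewhere: testing, self-testing, linkage, initiation, suppression, adherence and retention.

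**Step 4. The plan's own power figures.** These show that four outcomes are each powered at the full 5%. With n the effective number per arm and p̄ the mean of the two proportions,

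power = Φ{ [|p₁ − p₂| − 1.96·√(2p̄(1 − p̄)/n)] / √[(p₁(1 − p₁) + p₂(1 − p₂))/n] }.

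- Aim 1 (Protocol 1.2): 70 × 7 = 490 per arm; design effect 1 + 6 × 0.15 = 1.9; n = 257.9; 38% v 52% gives 89.4% (stated: at least 80%).
- Aim 2: same n; 24% v 39% gives 95.8% (stated: at least 80%).
- Aim 3 composite: 168 + 72 = 240 men, taken as 120 per arm (an assumption); n = 120/1.7 = 70.6; 70% v 89% gives 80.5% (stated: at least 80%).
- Retention: same n; 81% v 96% gives 80.4%, or 82.0% with unpooled variance (stated: 81%).

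All four meet or reproduce the stated figures. Retention is therefore treated in the power section as a full primary outcome.

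**Step 5. Scale of the error rate.** Neither document states a family-wise figure. For k independent tests at 5%, the chance of at least one false positive is 1 − 0.95^k:

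- k = 3: 1 − 0.8574 = 14.3% (upper bound under any dependence 15%)
- k = 5: 1 − 0.7738 = 22.6% (upper bound 25%)

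Several of the outcomes are nested: initiation follows linkage, and retention requires initiation. Positive correlation probably puts the true values below the independence figures.

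**The case against.** The other side has several fair points.

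- **The SAP's numbering points to three.** Testing, linkage and the composite are called first, second and third primary outcome, which matches Protocol 1.3.2–1.3.3. Self-testing is called only the second outcome, without the word primary, so its place may be a slip. This shows the probable intent and supports the fix. It does not settle the heading it sits under, or the self-testing comparison in SAP 27.
- **Suppression and adherence concern different men.** The synopsis may simply be naming the two parts of the composite. This is the weakest of the conflicts.
- **Three aims with separate hypotheses can be tested unadjusted.** That stands. A reader might infer that adjustment is mandatory; nothing here shows that.
- **The label is not the only safeguard.** The SAP also fixes the test for each aim, an intention-to-treat population, missing as failure, and confidence intervals with exact p-values. That stands too, but none of these says which outcome is primary.
- **The SAP relies on protocol version 4.0.** A reader might infer that the statement in SAP 17 is false. That cannot be shown, because version 4.0 may have held one list, and the self-testing and 12-month differences may come from the change of version. The initiation and retention conflicts within protocol 11.0, and the retention conflict within the SAP, do not depend on this.

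**Conclusion.** The point holds as a conflict of labels and time points within each document and between them. The clearest cases are initiation (Protocol 1.1 against the synopsis and 1.3.3) and retention (Protocol 1.2 against 1.3.3; SAP 11 against 26.b). The Aim 1 test in SAP 27 and the composite's time point also need settling. SAP 17's reason for not adjusting leans on a single primary set that the supplied protocol does not give.

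The scale, 14% to 23% for three to five tests, assumes independence and is illustrative. A reader might go further and speak of seven primary outcomes and a 30% error rate (1 − 0.95^7 = 0.302). The documents do not support that: no written list has more than five, seven is a union across sections, and several of those outcomes are nested. The matter should be corrected, but it does not call the design or sample size into question.

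**What to change.** State one primary list, in the same words, in the synopsis, Protocol 1.1, 1.2, 1.3.1 and 1.3.3, and SAP 11, 26 and 27:

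1. any self-reported HIV testing at 3 months;
2. linkage within 3 months of intervention start;
3. the suppression/adherence composite at 6 months, the time point in Protocol 1.1 and 1.3.3.

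Make initiation, retention, self-test kit use, the separate components of the composite and any 12-month measure secondary. In SAP 27, change the Aim 1 comparison from self-testing to any HIV testing. Update the protocol version cited in SAP 3, and reword SAP 17 so that its reason refers to this list.

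The cost is wording in these sections and the loss of the primary label for some results. Design, sample size and data collection do not change. The fix requires no multiplicity adjustment. If one were wanted, it would have a price: dividing 5% by three (0.0167 per test) lowers Aim 3 power from 80.5% to 66.0% on the plan's own assumptions.
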